Relevance	
Among the challenges of ASCVD, preventing recurrent MACCEs is a significant issue. Scientific evidence widely supports pharmacotherapeutic approaches for the routine use of a P2Y12 inhibitor (clopidogrel or an alternative) within the framework of DAPT or other regimens of antiplatelet treatment. Clopidogrel remains the most commonly used P2Y12 inhibitor in the post-PCI setting. Pharmacogenetic models of drug selection are also being introduced to optimize treatment.
 
Currently, the selection of treatment with clopidogrel or an alternative P2Y12 inhibitor by genotyping CYP2C19 alleles is based on reliable evidence. The effects of treatment are influenced by the wide variability of CYP2C19 genotype in the population, which, even under conventional treatment with clopidogrel, significantly increases the risk of MACCEs in carriers of non-functional alleles.
 
The antiplatelet treatment paradigm faces a significant dilemma regarding the use of clopidogrel: on the one hand, existing practice guidelines (ESCARDIO and ACC/AHA) recommend the use of clopidogrel without CYP2C19 genotyping. On the other hand, the Global Consensus Report of Industry Associations on the Possibility of Adapting P2Y12 Inhibitor Treatment to CYP2C19 Genotyping and the Selective Use of the Test (2019), as well as the FDA's so-called "black box warnings" on the use of clopidogrel, the EMA's precautionary statements, the CPIC and DPWG scientific reports and practice guidelines, and the evidence base UNC study, TAILOR-PCI, POPular Genetics, PHARMA-ACS, UK Biobank study, and other so-called "From New Prospective Studies" clearly demonstrates the advantages for guiding P2Y12 inhibitor treatment by CYP2C19 genotype.
 
In these circumstances, promising research directions are determined by the following critical questions: Is it possible to select P2Y12 inhibitor treatment by genotype? This issue will be resolved by answering the main question: Are CYP2C19 genetic variations associated with clinical outcomes of clopidogrel treatment, in interaction with other known influencing factors or independently of them?

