Hypothesis	
The research question is how antiplatelet treatment for preventing major adverse cardiovascular events after ePCI works in chronic coronary artery disease when guided by personal genetic characteristics for drug metabolism.
 
The study aims to test two research hypotheses:
 
 
• CYP2C19 genotype-guided clopidogrel treatment ensures better clinical outcomes when compared with conventional treatment selection led without CYP2C19 genotyping.
 
• CYP2C19 genotype-guided antiplatelet treatment could be beneficially applied in real-world clinical practice.
 

Design	Multicenter, randomized, parallel-group controlled study

Primary Objectives	
The aim of the study is to evaluate CYP2C19 allele genotype-guided antiplatelet treatment outcomes.
 
The specific objectives of the study are:
 
 
— Pre-assignment and randomization of study participants into study arms for conventional and CYP2C19 genotype-guided antiplatelet treatment with clopidogrel or an alternative P2Y12 inhibitor;
 
— providing RT-PCR-based pre-, analytical and post-analytical processes of the study to ensure CYP2C19 *2, *3 allele profiling for detection of study participants with normal functioning (NFA) and loss of function (LOF) allele;
 
— Observation of clinical outcomes of patients in the study groups during the 12 months of treatment;
 
— Evaluation of processes and non-clinical outcomes of clinical case management;
 

Secondary Objectives	
 
— Implementation of the methods and procedures provided by the research protocol into a real clinical practice pipeline;
 
— Raising awareness and understanding of the role of laboratory services by bridging clinical, laboratory practice professionals and other stakeholders to achieve patient-centeredness and improve clinical outcomes;
 
— Evaluation of clinical practice models based on assessments of molecular markers;
 
— Disseminate study results through publishing a scientific paper in a peer-reviewed journal and abstracts for reporting study results.
 

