The current paradigm for clopidogrel use faces a dilemma. Existing practice guidelines (ESCARDIO, 2017 and ACC/AHA, 2016) provide recommendations for the use of clopidogrel or other P2Y12 inhibitor treatment without CYP2C19 genotyping. A larger evidence base supporting the efficacy of the pharmacogenetic approach is required to guide treatment recommendations based on CYP2C19 genotyping, including genome-wide associations between CYP2C19 genotype variability and MACCE of recurrent ASCVD on clopidogrel treatment [8, 10]. On the other hand, the 2019 Global Consensus Report of the industry associations presented the possibility of tailoring P2Y12 inhibitor treatment based on CYP2C19 genotype and general recommendations for the selective use of CYP2C19 genetic testing [10]. The FDA's so-called "Clopidogrel" "Black box warnings" [18], EMA precautionary statements, CPIC and DPWG scientific reports [19-21], as well as the evidence base from new pragmatic and prospective studies [9-16], support the approach of CYP2C19 allele-specific P2Y12 inhibitor treatment and determine its efficacy. Approximately 30% of the European population and 60% of Asians carry CYP2C19 non-functional alleles [21], which are associated with resistance to clopidogrel treatment and a significantly increased risk of MACCE [21-24].

At this stage, the directions of scientific development can be determined by the following research questions: Can CYP2C19 allele genotypes be routinely used for P2Y12 inhibitor treatment? The answer to the main question will make a significant contribution to resolving this issue: Are CYP2C19 genetic variations associated with clinical outcomes of clopidogrel treatment independent of interactions with other known factors?

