### 2.3.2 Structural Design

Study participants will be recruited from 4 or more clinical centers. Based on informed consent, these centers will be selected and employed to provide study-specific activities under the condition that they provide CAD-specific diagnostic, treatment, and prevention services as recommended by current guidelines in their real-world clinical practice. They must provide GCP-compliant care based on current quality standards, patient best interests, and safety.

A logical model of study.

A population of patients who require antiplatelet therapy with a P2Y12 inhibitor following ePCI in CAD CCS cases within the framework of the recommendations for the use of DAPT (ESC, ACC/AHA) will be pre-assigned from the centers' real-world practice. Eligible patients will be considered for participation in the study after formal informed consent for inclusion in the specific clinical study measures.

Screening measures will be implemented for these patients to establish study inclusion and exclusion criteria. In conditions of the existence of inclusion criteria and absence of exclusion criteria, study participants will be randomized to the study or control arm by control-to-experiment allocation rate 1:2.

Study participants randomly allocated to the experimental arm will undergo laboratory blood testing for CYP2C19 \*2, \*3 genotyping using the RT-PCR-based allele discrimination method. According to the results of genotyping, the study participants will be assigned to two experimental treatment arms:

1st experimental arm will consist of the study participants with the active metabolizing phenotype of CYP2C19 (a normal function CYP2C19 \*2, \*3 allele (NFA) genotype), who will receive clopidogrel-based antiplatelet treatment;

2nd experimental arm will consist of study participants with the passive metabolizing phenotype of CYP2C19 (a loss-of-function CYP2C19 \*2, \*3 allele (LOF) genotype, heterozygous or homozygous), who will receive alternative antiplatelet treatment of clopidogrel.

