Study participants allocated to the control arm – 3rd arm of active comparators will not undergo laboratory blood testing for CYP2C19 \*2, \*3 genotyping, will be considered as study participants with unspecified metabolizing phenotype of CYP2C19 and receive the P2Y12 inhibitor clopidogrel-based antiplatelet treatment according to current clinical practice recommendations, without genotyping for CYP2C19 \*2, \*3 alleles as by real-world practice.

All study participants assigned to the study arms will undergo baseline and ongoing clinical follow-up to assess clinical endpoints as study clinical outcomes.

All clinical cases will be followed up with the primary, secondary and other prespecified clinical endpoints of the study and routine clinical indicators of safety at 3, 6, and 12 months. Non-clinical study outcomes will be assessed and compiled with other results of the outcome measures.

Study monitoring and evaluation procedures will be implemented alongside the study activities to assess safety and efficacy, and outputs.

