2nd arm - experimental: "Passive Metabolizers of Clopidogrel", approximately† 50 study participants diagnosed with chronic coronary artery disease who had undergone elective PCI, tested with CYP2C19 genotyping, identified as LOF \*2, \*3 allele carriers, who undergo CYP2C19 Genotype Guided Antiplatelet Treatment Alternative to Clopidogrel - an antiplatelet drug alternative to clopidogrel in conventional dosing regimen, as a component of preventive antiplatelet treatment, such as double antiplatelet treatment (DAPT) with ticagrelor or prasugrel, or prasugrel combined with the nonvitamin K antagonist oral anticoagulants (NOAC), or antiplatelet monotherapy (ticagrelor, or prasugrel).

3rd arm - active comparator: "Unspecified Metabolizers of Clopidogrel", 80 participants diagnosed with chronic coronary artery disease who had undergone elective PCI were allocated to the arm, without CYP2C19 genotyping through simple randomization, and having an unspecified metabolism phenotype, who were assigned to the conventional clopidogrel treatment - clopidogrel as a component of preventive antiplatelet treatment, such as double antiplatelet treatment (DAPT), or clopidogrel combined with the non-vitamin K antagonist oral anticoagulants (NOAC), incl. triple antiplatelet treatment (Aspirin, Clopidogrel and a NOAC), or antiplatelet monotherapy (Clopidogrel).

† The prevalence of carriers of CYP2C19 \*2, \*3 non-functional alleles in the Georgian population has not been studied and is unknown. To estimate the number of patients in subgroup II arm 1 and arm 2, we used the extrapolation of known data from a European population study [12].

2 study arms could be used as control for analyzing and comparing study outcome measures: 3rd study arm participants create the active comparators' group for 1st and 2nd arm, and besides, 2nd study arm participants - as the comparators for 1st arm:

Control 1: "Normal Metabolizers of Clopidogrel" - 110 study participants vs "Unspecified Metabolizers of Clopidogrel" - 80 participants;

Control 2: "Passive Metabolizers of Clopidogrel" - approximately 50 participants vs "Unspecified Metabolizers of Clopidogrel" - 80 participants;

Control 3: "Normal Metabolizers of Clopidogrel" - 110 study participants vs "Passive Metabolizers of Clopidogrel" - approximately 50 participants.

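### The stated main question, whether CYP2C19 variants are associated with outcomes on clopidogrel, gets no direct data from this design, and Control 3 changes genotype and drug together

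*Combined protocol and SAP*

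**What the plan says.** **The question.** The Synopsis (Relevance) asks whether P2Y12 inhibitor treatment can be selected by genotype and adds: "This issue will be resolved by answering the main question". That question concerns "genetic variations associated with clinical outcomes of clopidogrel treatment, in interaction with other known influencing factors or independently of them". Section 1.3 repeats it in a narrower form: "Are CYP2C19 genetic variations associated with clinical outcomes of clopidogrel treatment independent of interactions with other known factors".

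**The formal aim.** The Synopsis (Hypothesis) states a strategy comparison: "genotype-guided clopidogrel treatment ensures better clinical outcomes when compared with conventional treatment selection" made without genotyping. The aim in section 1.4.1 is likewise about outcomes of genotype-guided treatment.

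**The arms.** Under section 2.3.2, arm 1 (normal-function genotype) is the group "who will receive clopidogrel-based antiplatelet treatment". Arm 2 (LOF genotype) is the group "who will receive alternative antiplatelet treatment of clopidogrel". Arm 3 receives clopidogrel, is not genotyped, and its participants "will be considered as study participants with unspecified metabolizing phenotype of CYP2C19". Section 2.4.4 accepts that LOF status in the control arm cannot be assessed. The data-sharing text in section 7.2 lists allele profiles for the intervention group only.

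**The comparisons.** The Synopsis (Controls) and section 2.4.2 allow arm 3 to serve as comparator for arms 1 and 2, "and besides, 2nd study arm participants - as the comparators for 1st arm". This last comparison is Control 3. The Synopsis (Primary statistical analysis) has one experimental frequency and two control frequencies, Rc1 and Rc2. Section 2.5.7 labels the LOF arm a comparator and the ungenotyped arm experimental. Section 2.6.3 instead has two experimental frequencies (Rt1, Rt2) and one comparator (Rc). Appendix 3 tabulates effect measures only for arm 1 against arm 3 and for arms 1+2 against arm 3.

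**The concern.** To see directly whether a variant matters on clopidogrel, one needs carriers and non-carriers who both take clopidogrel and whose genotype is known. This plan has only the non-carriers. Among genotyped participants, genotype determines the drug.

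Control 3 is the only listed contrast between two groups of known genotype, so it is where a reader would look for an answer. Similar event rates in arms 1 and 2 could be taken to mean that genotype does not matter, and different rates to mean that it does. Neither follows. The contrast is no better as evidence on the drugs, because the people taking them differ in genotype by construction.

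**Working it through.** **1. The plan's own figures.** The second sample-size tool (section 2.6.2) uses 0.6 v 0.4, 2:1 allocation, two-sided 0.05 and power 0.8. With pooled variance and no continuity correction, the control group needs

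[1.96·√(1.5 × 0.4667 × 0.5333) + 0.8416·√(0.24 + 0.24/2)]² / 0.2² = (1.1976 + 0.5050)²/0.04 = 72.5, so 73.

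The total is 73 + 146 = 219, against a stated 221. The figure reproduces closely and is not in dispute. It concerns experimental v control, not genotype within clopidogrel. The arm 2 size also fits: 160 × 0.30 = 48, against about 50.

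**2. What is observed.**

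| Cell | Clopidogrel | Alternative drug |
|---|---|---|
| Known normal function | 110 | 0 |
| Known LOF | 0 | about 50 |
| Not genotyped | 80 | 0 |

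With q = 50/160 = 0.3125, about 80 × 0.3125 = 25 controls would be LOF carriers on clopidogrel, but none can be identified.

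**3. Control 3.** Write pN for the risk of normal-function patients on clopidogrel, pL for LOF carriers on clopidogrel, and pA for LOF carriers on the alternative. Then

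R2 − R1 = (pA − pL) + (pL − pN).

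The first term is the drug effect in carriers and the second is the genotype effect on clopidogrel. One observed number cannot separate two unknowns, and a regression cannot either, since the cells are 110/0 and 0/50. As an illustration with assumed risks, pN = 5%, pL = 10% and pA = 5% give R2 − R1 = 0. So do pN = pL = pA = 5%. A harmful variant offset by an effective drug looks the same as no effect of either.

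**4. The indirect route.** Randomisation gives arm 3 the same expected genotype mix as the guided group:

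R3 = (1 − q)pN + q·pL, and R1 estimates pN, so pL − pN = (R3 − R1)/q.

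Both parts are already in Appendix 3. The absolute benefit for genotype-guided clopidogrel is R3 − R1, and the LOF percentage among those tested is q. Because q is observed in the trial, the unknown Georgian prevalence is not an obstacle. The approximate standard error is

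SE = √[R3(1 − R3)/80 + R1(1 − R1)/110] / q.

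- Assumed 5% and 10%, q = 0.3125: R3 = 0.6875 × 0.05 + 0.3125 × 0.10 = 0.0656. SE = √(0.0656 × 0.9344/80 + 0.05 × 0.95/110)/0.3125 = 0.111. The 95% half-width is 1.96 × 0.111, about 22 points, for a true difference of 5.
- Assumed 10% and 20%, q = 0.30: R3 = 0.13. SE = √(0.13 × 0.87/80 + 0.10 × 0.90/110)/0.30 = 0.157. The half-width is about 31 points, for a true difference of 10.

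Sampling error in q hardly matters. In the first case it contributes 0.05 × √(0.3125 × 0.6875/160)/0.3125 = 0.006, and the combined SE is still 0.111.

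Dropout does matter. If only the 75% expected to complete (section 2.4.2) contributed, the half-widths would grow by 1/√0.75 = 1.155, to about 25 and 36 points.

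**5. Power of arm 1 v arm 3 for the variant effect.** In arm 3 a LOF relative risk is diluted to 1 + q(RR − 1). At q = 0.30, RR 2 becomes 1.3 and RR 3 becomes 1.6. With RR 2, power at 110 v 80 is about 7% for a normal-function risk of 5% and about 10% for a risk of 10%. Both risks lie within the 1–10% that section 3.2.1 gives for MACCE.

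**The case against.** The strongest reply is that the plan does not promise to answer this question. It stands in Relevance text about directions for the field, and no objective, hypothesis, endpoint or analysis takes it up. The aim and hypotheses already concern the guided strategy. Moving LOF carriers off clopidogrel is the intervention itself, so having no known carriers on clopidogrel is inherent to such a trial. Control 3 is only something that could be used, and the detailed indicator list contains no arm 1 v arm 2 effect measure.

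Most of that stands, and it limits the weight of the point. What remains is that two passages call this the main question, that Control 3 is a listed comparison, and that the Synopsis frequencies and the arm labels in section 2.5.7 point towards using arm 2 as a control.

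Three stronger readings are tempting, and the documents do not support them:

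- *The trial cannot meet its aim.* It can address it: arms 1+2 v arm 3 is a randomised comparison and is specified throughout Appendix 3.
- *The association cannot be studied at all.* Arm 1 v arm 3 holds the drug constant and carries indirect information, as shown in the working.
- *The plan intends Control 3 as proof of a genotype effect.* No passage says so. The misreading is a risk, not a stated analysis.

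A reader might also infer that the controls should be genotyped. With 25 identified carriers and 165 normal-function patients (110 + 55), the SE at 5% and 10% would be √(0.10 × 0.90/25 + 0.05 × 0.95/165) = 0.062, or about ±12 points for an assumed difference of 5. That gain does not justify some 80 tests beyond the planned 160, new consent wording, and storage that departs from the rule in section 2.5.8 that genotyping samples are destroyed after analysis.

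**Conclusion.** The point holds in limited form. The plan names the variant–outcome association on clopidogrel as the main question but collects no direct data on it: 110 known normal-function participants and no known LOF carriers are assigned clopidogrel. Control 3 confounds genotype with drug and supports no conclusion about either.

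The indirect estimate is valid under randomisation if open-label knowledge of genotype (section 2.5.4 discloses results to participants and the care team) does not itself change outcomes. It is too imprecise to settle the question, with a half-width of about 22 to 31 percentage points before dropout. The risks behind those widths are assumptions, since the documents give no LOF effect size for this population.

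This is a correction of wording and of one listed contrast. It is not a flaw in the randomised strategy comparison.

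**What to change.** 1. In the Synopsis (Relevance) and section 1.3, replace the main question with the strategy question already in the Synopsis (Hypothesis) and section 1.4.1: genotype-guided selection v clopidogrel without genotyping. This also removes the difference between the two versions over interaction with other factors.
2. In the Synopsis (Controls) and section 2.4.2, remove Control 3 as an inferential contrast and report arm 1 and arm 2 side by side, descriptively. Reconcile Rc1/Rc2 in the Synopsis and the arm labels in section 2.5.7 with section 2.6.3 and Appendix 3.
3. If the association is kept, add one line to section 2.6.3: estimate it as (R3 − R1)/q with a 95% confidence interval, labelled exploratory, stating the open-label assumption and the expected imprecision.

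The cost is a few edits and at most one formula built from quantities already planned. No new data, tests or consent are needed, and no tabulated indicator is lost. The price is that one prominent question is dropped or answered with a wide interval.

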## **1.4. Study Objectives**

### **1.4.1. Primary Objectives**

The aim of the study is to evaluate CYP2C19 allele genotype-guided antiplatelet treatment outcomes.

The specific objectives of the study are:

- Pre-assignment and randomization of study participants into study arms for conventional and CYP2C19 genotype-guided antiplatelet treatment with clopidogrel or an alternative P2Y12 inhibitor;
- providing RT-PCR-based pre-, analytical and post-analytical processes of the study to ensure CYP2C19 \*2, \*3 allele profiling for detection of study participants with normal functioning (NFA) and loss of function (LOF) allele;
- Observation of clinical outcomes of patients in the study groups during the 12 months of treatment;
- Evaluation of processes and non-clinical outcomes of clinical case management;

By responding to these objectives, the effectiveness of CYP2C19 genotype-guided clopidogrel treatment in selected cases will be assessed, clinical approaches for the use of CYP2C19 genotyping in existing, real-world clinical practice will be determined, the implementation of treatment measures tailored to the results of CYP2C19 genotype testing will be analyzed, and the possibilities of using these approaches in real-world clinical practice for treatment personalization will be analyzed.

#### **1.4.2 Secondary Objectives**

Secondary objectives are set to explore and evaluate opportunities for implementing research findings:

- Implementation of the methods and procedures provided by the research protocol into a real clinical practice pipeline;
- Raising awareness and understanding of the role of laboratory services by bridging clinical, laboratory practice professionals and other stakeholders to achieve patient-centeredness and improve clinical outcomes;
- Evaluation of clinical practice models based on assessments of molecular markers;
- Disseminate study results through publishing a scientific paper in a peer-reviewed journal and abstracts for reporting study results.

By responding to these objectives, the feasibility and applicability of the clinical and laboratory procedures for CYP2C19 genotype-guided treatment selection to optimize the treatment with clopidogrel or alternative P2Y12 inhibitors in real clinical practice will be assessed, obstacles and acceptability of the studied approaches by stakeholders groups will be determined, the perception of the problems will be strengthened, and the effectiveness of the use of dissemination channels for research results will be determined.

#### **1.4.3 Expected Duration of the Study**

The total expected duration of the study is 24 months. The implementation will conditionally include 4 stages.

Preparatory work will be carried out during the first 2 months of the project implementation to initiate the study.

[figure not shown]
The expected duration of the study component itself is 20 months from the screening/randomization of the first study participant to the end point of observation of the last involved study participant.

During this period, the inclusion of participants in the study will continue for approximately 8 months.

Follow-up visits and relevant examinations will begin 1 month after the inclusion of the first patient, which will continue for 12 months after the inclusion of the last participant in the study and continue throughout the follow-up of clinical outcomes and related clinical case management processes.

The analysis of the final results of the study, the formulation of assessments, the preparation of the scientific paper, submission for peer-reviewed publications and the preparation of the final scientific and technical reports of the study will be carried out during the last 2 months of the project.

Monitoring and evaluation activities will be carried out throughout the 24-month project period.

The overall duration of the research project can be reduced by condensing the study components separately. In particular, the intensification of study participants' enrolment activities can be achieved by increasing the frequency (accelerating) of study participants' screening, pre-assignment and randomization in study centers and, accordingly, by shifting the calendar end of the follow-up component period. In such a case, it is expected that the reasonable duration of the calendar term for the study activities for study participants enrollment will be 6 months instead of 8 months, and accordingly, by shifting the calendar end of the 12-month follow-up period, the overall duration of the research project will be shortened up to 22 months instead of 24 months.

